11.5 Lost to Follow-up

If a patient is lost to follow-up, a Patient Disposition CRF must be completed. If a patient fails to comply with follow-up evaluations, the study center must make repeated attempts (at least three) to contact the patient. Each attempt to contact the patient and the method used (e.g., telephone contact, registered letter) must be documented in the patient's records. Also, a letter to the patient's general practitioner will be sent informing him/her that his/her patient was lost to follow-up.

11.6 Patient Withdrawal from the Study

11.6.1 Voluntary Withdrawal

A patient may voluntarily withdraw from the study at any time. The Patient Disposition CRF must be completed. If the patient has experienced an AE, where possible the patient should be followed until its resolution.

11.6.2 Withdrawal for Other Reasons OR Non-Treatment

If the patient has signed the ICF but was later found to not meet inclusion/exclusion criteria prior to enrollment or deemed not suitable for treatment by the physician the patient will not be considered enrolled in the study.

11.6.3 End of Study

Patients will exit the study at the time the study is closed or after the 30 day of follow up, whichever comes first. Patients may also exit the study by withdrawing his/her participation voluntarily. A Patient Disposition CRF is required at the time of study completion or discontinuation for all enrolled patients.

12. DATA RECORDING AND SUBMISSION REQUIREMENTS

Data

All aspects of the study will maintain patient privacy and be Declaration of Helsinki and General Data Protection Regulation (GDPR) and Data Protection Act 2018 compliant.

All **raw data** will be entered into an Excel or validated spreadsheet format (with patient names excluded) and include all data collected on the patients up to the time the data is frozen including baseline, procedure, and all follow up data available. All data sets provided shall be clean with all queries resolved.

The following are the types of data in the study:

RAW DATA:

1. PEPNS System electronic archive – data recording by the PEPNS system will be electronically archived by Stimdia Medical.
2. Patient history file – this document will confirm patient meets inclusion and exclusion criteria while also documenting all demographic and physiology aspects of the enrolled patient.
3. PEPNS System procedure report – documentation of procedure related information, e.g., sedation, ventilation, stimulation, ultrasound, test article documentation, procedure step checklist and procedure related specifics noted.

CASE REPORT FORMS (CRF):

1. Screening form
2. Index procedure form
3. Adverse event form
4. Patient disposition form
5. Protocol deviation form
6. Device malfunction form
7. Follow up form

SPREADSHEET AND ANALYSES:

1. All data relevant to analysis will be maintained in a validated Excel spreadsheet until the completion of the study. The master spreadsheet will be validated and maintained by Stimdia Medical. All Excel files used for the data analysis must be password protected and only authorized study personnel can have access to the passwords.

Interim analysis and results will be reviewed with the steering committee in a periodic manner.

13. RISK/BENEFIT ANALYSIS

An analysis of the risks associated with the intended use of the device was undertaken according to the guidelines laid down in the standard EN ISO 14971:2012, Medical Devices – application of Risk Management to Medical Device. A complete Risk Assessment has been documented and resides within the design history file.

13.1 Potential Risks

The potential risks related to the PEPNS System and procedure may include but are not limited to the following:

1. Blood loss > 10 mL
2. Burn
3. Cardiac pacing
4. Diaphragm fatigue
5. Infection
6. Inflammation
7. Nerve damage
8. Pain
9. Pneumothorax (punctured lung)
10. Procedure failure
11. Scar
12. Vagus nerve stimulation, potentially resulting in asystole or bradycardia

The risks were mitigated to an acceptable level by design, fault detection, use of standards, training and labeling. The use of this device is considered to be relatively benign and testing performed so far in animals has confirmed this.

There are also some potential risks due to the mechanical ventilation and underlying patient comorbidities such as the following:

1. Barotrauma / volutrauma
2. Hypercarbia
3. Hypoxia

There may also be other risks related to use of the PEPNS System and procedure that are not listed or that are not known at this time. This study will help characterize the risks associated with the PEPNS System.

13.2 Minimization of Risk

To minimize the risks, the PEPNS System has undergone extensive pre-clinical and bench testing. In addition, all Investigators will undergo training on the PEPNS System and procedure and subjects will be screened and evaluated for medical histories/conditions that may compromise successful performance of the PEPNS System.

13.3 Potential Benefits

Up to 40% of patients admitted to intensive care units (ICUs) may require mechanical ventilation (MV) due to acute respiratory failure (ARF) or acute or chronic respiratory failure (ACRF), and this need is increasing. Most ACRF patients and, to a lesser extent, some patients with *de novo* ARF, may be treated with noninvasive MV, whereas a minority of these patients in the ICU need invasive MV. There is evidence that 65–85% of these patients undergoing invasive MV, under appropriate clinical conditions, can be successfully extubated, whereas up to 20% of patients will need a prolonged ICU length of stay (LOS) due to difficult weaning. This therapy has the potential to reduce the LOS for these difficult to wean patient by accelerating the time to wean by maintain diaphragm strength during sedation.

The proposed study is a first in human study (FIH) which will help define a pivotal study which will be needed for the regulatory approval of this device. During use of this device patients will have their diaphragms exercised

and it is believed that diaphragm strength may be maintained or increased. The study will provide real world data for design and validation for the safety and operational use of the PEPNS system.

SAFETY REPORTING

13.4 Definitions In Line with EN ISO 14155 Unless Otherwise Denoted

13.4.1 Adverse events (AE)

An adverse event is any untoward medical occurrence, unintended disease or injury, or untoward clinical signs (including abnormal laboratory findings) in subjects, users or other persons, whether or not related to the investigational medical device.

Notes:

- This definition includes events related to the investigational medical device.
- This definition includes events related to the procedures involved.
- For users or other persons, this definition is restricted to events related to investigational devices.

13.4.2 Serious adverse events (SAE)

A serious adverse event is an adverse event that:

- Led to death,
- Led to serious deterioration in the health of the subject, that either resulted in
 - a life-threatening illness or injury, or
 - a permanent impairment of a body structure or a body function, or
 - in-patient or prolonged hospitalization, or
 - medical or surgical intervention to prevent life-threatening illness or injury or permanent impairment to a body structure or a body function,
- Led to fetal distress, fetal death or a congenital abnormality or birth defect.

Note: Planned hospitalization for a pre-existing condition, or a procedure required by the protocol, without serious deterioration in health, is not considered a serious adverse event.

13.4.3 Adverse device effect (ADE)

Adverse event related to the use of an investigational medical device.

Notes:

- This definition includes adverse events resulting from insufficient or inadequate instructions for use, deployment, implantation, installation, or operation, or any malfunction of the investigational medical device.
- This definition includes any event resulting from use error or from intentional misuse of the investigational medical device.

13.4.4 Serious adverse device effect (SADE)

Adverse device effect that has resulted in any of the consequences characteristic of a serious adverse event

13.4.5 Unanticipated serious adverse device effect (USADE)

Serious adverse device effect, which by its nature, incidence, severity or outcome has not been identified in the current version of the risk analysis report

Note: Anticipated serious adverse device effect is a serious adverse device effect which by its nature, incidence, severity or outcome has been identified in the risk analysis report.

13.4.6 Device Deficiency

A device deficiency is an inadequacy of an investigational medical device with respect to its identity, quality, durability, reliability, safety or performance.

Note: Device deficiencies include malfunctions, use errors, and inadequate labeling.

13.4.7 Malfunction

Failure of an investigational medical device to perform in accordance with its intended purpose when used in accordance with the instructions for use or protocol.

13.4.8 Use error

Act or omission of an act that results in a different medical device response than intended by the manufacturer or expected by the user

Notes:

- Use error includes slips, lapses, and mistakes.
- An unexpected physiological response of the subject does not in itself constitute a use error.

13.4.9 List of Anticipated Adverse Events

See section 13.1 for a list of anticipated adverse events.

13.5 Adverse Event Classification

The severity of all adverse events and their relationship to the investigational device/study procedures will be classified by the investigator and reviewed by the steering committee or a clinical events committee. This review will include indication of any actions recommended be taken to protect patient safety and/or maintain data integrity.

13.5.1 Assessment of Adverse Event Relationship to Investigational Device

Investigators are required to assess whether there is a reasonable possibility that the Investigational Device caused or contributed to an SAE. Sponsor defines four degrees of relatedness: not related, unlikely, possible, probable, possible and causally related to the Investigational Device. The following definitions will be used to assess the relationship of the SAE to use of the Investigational Device per MEDEV 2.7/3 revisions 3 May 2015:

	
The relationship to the device or procedures can be excluded when:
 
• the event is not a known side effect of the product category the device belongs to or of similar devices and procedures;• the event has no temporal relationship with the use of the investigational device or the procedures;• the serious event does not follow a known response pattern to the medical device (if the response pattern is previously known) and is biologically implausible;• the discontinuation of medical device application or the reduction of the level of activation/exposure - when clinically feasible – and reintroduction of its use (or increase of the level of activation/exposure), do not impact on the serious event;• the event involves a body-site or an organ not expected to be affected by the device or procedure;• the serious event can be attributed to another cause (e.g. an underlying or concurrent illness/ clinical condition, an effect of another device, drug, treatment or other risk factors);• the event does not depend on a false result given by the investigational device used for diagnosis, when applicable;
Not Related	

	
 • harms to the subject are not clearly due to use error; • In order to establish the non-relatedness, not all the criteria listed above might be met at the same time, depending on the type of device/ procedures and the serious event.
Unlikely	The relationship with the use of the investigational device is weak but cannot be ruled out completely. Alternative causes are also possible (e.g. an underlying or concurrent illness/ clinical condition or/and an effect of another device, drug or treatment). Cases where relatedness cannot be assessed or no information has been obtained should also be classified as possible.
Possible	The temporal sequence between use of the Investigational Device and the effect is such that the relationship is not unlikely or Subject's condition or concomitant therapy could have caused the AE.
Probable	The relationship with the use of the investigational device seems relevant and/or the event cannot be reasonably explained by another cause, but additional information may be obtained.
Causal Relationship	
The serious event is associated with the investigational device or with procedures beyond reasonable doubt when:
 
 • the event is a known side effect of the product category the device belongs to or of similar devices and procedures; • the event has a temporal relationship with investigational device use/application or procedures; • the event involves a body-site or organ that 
 - the investigational device or procedures are applied to; - the investigational device or procedures have an effect on; • the serious event follows a known response pattern to the medical device (if the response pattern is previously known); • the discontinuation of medical device application (or reduction of the level of activation/exposure) and reintroduction of its use (or increase of the level of activation/exposure), impact on the serious event (when clinically feasible); • other possible causes (e.g. an underlying or concurrent illness/ clinical condition or/and an effect of another device, drug or treatment) have been adequately ruled out; • harm to the subject is due to error in use; • the event depends on a false result given by the investigational device used for diagnosis, when applicable • In order to establish the relatedness, not all the criteria listed above might be met at the same time, depending on the type of device/procedures and the serious event.

The sponsor and the investigators will distinguish between the serious adverse events related to the investigational device and those related to the procedures (any procedure specific to the clinical investigation). An adverse event can be related both to procedures and the investigational device. Complications of procedures are considered not related if the said procedures would have been applied to the patients also in the absence of investigational device use/application.

In some particular cases the event may be not adequately assessed because information is insufficient or contradictory and/or the data cannot be verified or supplemented. The sponsor and the Investigators will make the maximum effort to define and categorize the event and avoid these situations. Where the sponsor remains uncertain about classifying the serious event, it should not exclude the relatedness and classify the event as "possible".

If any Serious Adverse Event is considered to be either “possibly”, “probably”, or ‘causally’ related to the use of the Investigational Device, that event will be classed as an SADE.

13.6 Adverse Event Severity

The Investigator will also evaluate the severity in compliance with International Conference of Harmonization (ICH) – Good Clinical Practice (CGP) guidelines according to definitions from the Common Terminology Criteria for Adverse Events (CTCAE) from the department of U.S. Department of Health and Human Services.²⁶ See below for the applicable definitions

Grade 1	Mild; asymptomatic or mild symptoms; clinical or diagnostic observations only; intervention not indicated.
Grade 2	Moderate; minimal, local or noninvasive intervention indicated; limiting age-appropriate instrumental activities of daily living (ADL). Instrumental ADL refer to preparing meals, shopping for groceries or clothes, using the telephone, managing money, etc.
Grade 3	Severe or medically significant but not immediately life-threatening; hospitalization or prolongation of hospitalization indicated; disabling; limiting self-care ADL. Self-care ADL refer to bathing, dressing and undressing, feeding self, using the toilet, taking medications, and not bedridden.
Grade 4	Life-threatening consequences; urgent intervention indicated.
Grade 5	Death related to AE.

These definitions are for descriptive purposes only and are independent of the judgment of whether an event is classified as an AE or an SAE.

13.6.1 Handling and Reporting of Adverse Events

Investigator will report “to the sponsor, without unjustified delay, all serious adverse events and device deficiencies that could have led to a serious adverse device effect; this information shall be promptly followed by detailed written reports”. Device malfunctions and use errors should also be reported without unjustified delay.

All Serious Adverse Events (SA(D)Es) and/or device deficiencies must be reported to the Sponsor by telephone within 3 calendar days of the principal investigator becoming aware of it using the contact information below:

Reporting all Serious Adverse Events (SA(D)Es), including all device deficiencies can also be done by completing the CRF (AE/SAE and Device Deficiency forms) within 3 calendar days of event knowledge.

Where possible, Investigator will return the device involved in the deficiency to Sponsor for analysis.

Investigator will document all AEs on the Adverse Event Form, including (at a minimum) a description of the event, date of onset, severity, relationship to the investigational device and/or procedure, required interventions, duration, and outcome. The investigator will monitor all AEs until they are resolved, determined to be a chronic condition or the subject is lost to follow-up. Investigator will report all AEs regardless of whether it is anticipated or unanticipated and regardless of classification, seriousness, intensity, outcome or causality.

In the event of subject death, the investigator will make reasonable effort to obtain a copy of the autopsy report and/or death summary. The investigator will determine the cause of death and its relationship to the investigational device; Investigator will record results on the Adverse Event Form. The investigator will include copies of an autopsy report, if available, and/or a death summary with this form.

It is the responsibility of each Investigator to report all Serious Adverse Events and/or Serious Adverse Device Effects to the Local Ethics Committee in a timely manner, according to national regulations and Ethics Committee requirements. A copy of the Ethics Committee report should be forwarded to Sponsor.

13.6.2 Regulatory Authority Notification (If applicable)

Sponsor is responsible for the classification and reporting of serious adverse events and ongoing safety evaluation of the study in line with ICH-GCP/EN ISO 14155:2011/MEDDEV 2.7/3, Ireland's HPRA, the Czech Ministry of Health and other applicable regulatory requirements.

The sponsor will assess, together with the investigator, any serious adverse incidents arising from the investigation of the medical device and inform other investigators, HPRA and SUKL and the ethics committees thereabout immediately after their occurrence.

It is the obligation and responsibility of the Sponsor to report to HPRA and SUKL all serious adverse events, serious adverse device effects and/or unexpected serious adverse device effects received from a Principal Investigator within 2 calendar days after learning of the event.

The Sponsor will also inform the other participating Principal Investigators and ethics committees of all serious adverse events, serious adverse device effects and/or unanticipated adverse device effects that are reported within 3 calendar days after learning of the event.

13.6.3 Follow-up of Unresolved Events

All serious adverse events, serious adverse device effects and/or unexpected adverse device effects will be followed until they are resolved or until the subject's participation in the clinical investigation ends.

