16.2	Informed Consent and Patient Information	40
16.3	Protocol Deviations	40
16.4	Amendments.....	41
16.5	Investigational Device Accountability and Storage	41
16.6	Monitoring Plan.....	41
16.7	Indemnity.....	42
16.8	Insurance.....	42
16.9	Investigators Responsibilities	42
16.10	Sponsor Responsibilities	44
16.11	Statement of Compliance	46
16.12	Publication Policy.....	46
17.	REFERENCES.....	47

STUDY SUMMARY

PEPNS System Feasibility Study Summary	
Title	Percutaneous Electrical Phrenic Nerve Stimulation (PEPNS) System Feasibility Study
Short Title	PEPNS System Feasibility Study
Study Sponsor	
Stimdia Medical, Inc. Contacts: [name] President and CEO [contact] [contact]
 
[name] Vice President of Research and Development [contact] [contact]
 
[name] Clinical Study Director [contact] [contact]

Protocol Number & Version	CIP0001 Rev 4, November 30, 2018
Study Device	Percutaneous Electrical Phrenic Nerve Stimulation (PEPNS) System
Purpose	The purpose of this study is to evaluate the safety and performance of the PEPNS System in patients that need to be mechanically ventilated for at least 48 hours and up to 7 days in the Intensive Care Unit (ICU).
Study Design	Prospective; Non-randomized; Open-label
Enrollment	Up to 2 sites and up to 10 subjects per site. The very first 2 subjects will be stimulated on the left phrenic nerve and followed for 30 days prior to enrolling additional patients. In addition, compound muscle action potential testing (CMAP) and nerve conduction studies, will be conducted on the first 2 subjects during the index procedure and at or before the 30 day follow up.
Follow Up	All subjects will be followed up for 30 days after their index procedure for a total participation period of up to 41 days.
Estimated Study Duration	It is expected that up to 10 subjects will be enrolled per site (up to two sites) during the course of 4 to 6 months for a total estimated study duration of up to 18 months once both sites start to enroll subjects.
Study Population	Patients that need to be mechanically ventilated for at least 48 hours and up to 7 days in the Intensive Care Unit (ICU).

PEPNS System Feasibility Study Summary

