10. PROCEDURE DURATION AND FOLLOW-UP

Procedure Duration and Follow-up
Up to 48 hours of continuous stimulation time
Upon expiration of the 48 hour stimulation period the stimulation will be turned off and the PEPNS multipolar leads will be removed from the patient.

Patient Follow-up
Each patient will be followed for a total of 30 days after stimulation end to determine if he/she experienced any adverse events with a clinic follow-up visit and for a chest x-ray. This follow up may occur within +7 days of the 30-day follow-up period giving an allowable follow-up range of 30 to 37 days for AE's and 30 ± 7 days for the chest x-ray.

The total expected duration of the clinical trial is up to 18 months once both sites start to enroll subjects.

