11.3 Follow-Up Visits

All subjects will be followed up at 30 days to 37 days for adverse events and 30 ± 7 days for the chest x-ray. At this time hospital discharge and ventilation weaning time data will also be collected. Table 1 summarizes all required and optional test and procedures throughout the study including each visit's compliance windows.

Table 1: Study Procedures and Follow Up

Test / Evaluation	Screening (within 2 days pre-procedure)	Index procedure	30 day follow up
Signed Informed Consent	X		
Subject Demographics	X		
Medical History	X		
Height/Weight/BMI	X		
Blood Pressure	X		
Chest x-ray	X ¹		X
12 lead ECG		X	
Lead Insertion assessment		X	
1 hr. cessation of electrical stimulation		X	
Patient movement / repositioning assessment		X	
CMAP ²		X	X
CPOT/RASS assessments		X	
Muscle twitching observation		X	
Ultrasound screen shots (optional) Ventilation settings and end-tidal CO ₂ required Stimulation Data Vital Signs / pulse oximetry Standard Blood gases: pH, paO ₂ , PaCO ₂ etc. Diaphragm thickness (optional)		X	
Lead Removal assessment		X	
Adverse Events		X	X
Device Malfunctions		X	

¹ It is acceptable if this has been taken up to 30 days prior to the screening visit.

² Only for the first 2 patients enrolled.

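### Protocol sections 13.6.1, 13.6.3 and 11.6.1 give different stop rules for adverse events still open when a patient leaves the study, and nothing says which governs a serious one.

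*Protocol*

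**What the plan says.** Three sections of the protocol say when follow-up of an adverse event stops.

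- Section 13.6.1, on handling and reporting: "The investigator will monitor all AEs until they are resolved, determined to be a chronic condition or the subject is lost to follow-up". There is no calendar limit, and leaving the study is not one of the stops. The next sentence makes the breadth of the paragraph plain: "Investigator will report all AEs regardless of whether it is anticipated or unanticipated and regardless of classification, seriousness, intensity, outcome or causality". The same paragraph requires the duration and outcome of each event on the Adverse Event Form.
- Section 13.6.3, on unresolved events: serious adverse events, serious adverse device effects and unexpected adverse device effects "will be followed until they are resolved or until the subject's participation in the clinical investigation ends". Here the end of participation is a stop, and a finding that the event is chronic is not.
- Section 11.6.1, on voluntary withdrawal: a patient who leaves with an adverse event should, where possible, be followed until it resolves.

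Section 11.6.3 defines the end of participation: "Patients will exit the study at the time the study is closed or after the 30 day of follow up, whichever comes first". The SAP's Adverse Events paragraph plans the percentage of patients with a serious device- or procedure-related event and a note of the follow-up x-ray result. It does not say how an event still open at exit is handled.

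**The concern.** A serious adverse event is also an adverse event, so 13.6.1 and 13.6.3 both apply to it and end its follow-up at different points. A site could reasonably treat 13.6.3 as the specific provision, since its heading concerns unresolved events and it names the serious ones. On that reading a serious device effect may be closed at the exit visit, while a non-serious event in the next patient is still followed to resolution or a chronic state.

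The final outcome of a device-related injury is part of what a first-in-human study is meant to learn. Section 13.1 lists nerve damage among the potential risks, and one of the seriousness criteria in section 13.4.2 is "a permanent impairment of a body structure or a body function". CMAP and nerve conduction testing is planned only for the first two patients. For the others, the scheduled checks after treatment are adverse event review and a chest x-ray. If follow-up stops at exit, an unresolved nerve injury would stand in the record as ongoing, with neither the duration nor the final outcome that 13.6.1 asks for.

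**Working it through.** **Step 1. When does participation end?** The study summary gives the plan's own figure: "All subjects will be followed up for 30 days after their index procedure for a total participation period of up to 41 days". The inputs that reproduce it are:

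- screening up to 2 days before the procedure (Table 1 in section 11.3);
- stimulation for at most 48 hours, or 2 days (section 6);
- follow-up for 30 days after stimulation ends, with a 7-day allowance (section 10), "giving an allowable follow-up range of 30 to 37 days for AE's".

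The sum is 2 + 2 + (30 + 7) = 41 days, which matches. The latest scheduled exit is therefore 41 days from the start of screening, and the adverse event visit falls 30 to 37 days after stimulation ends. Section 11.6.3 allows an earlier exit if the study closes first. Section 6.6, however, keeps enrolled patients in follow-up for 30 days after an early termination, so the 30-day visit is the usual end point.

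**Step 2. The three rules side by side.**

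| | 13.6.1 | 13.6.3 | 11.6.1 |
|---|---|---|---|
| Events covered | all adverse events | serious events, serious device effects, unexpected device effects | any adverse event in a patient who withdraws |
| Stops on resolution | yes | yes | yes |
| Stops when judged chronic | yes | not stated | not stated |
| Stops on loss to follow-up | yes | not stated | not stated (where possible) |
| Stops when participation ends | not stated | yes | no; it applies after the patient has left |

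**Step 3. Apply the rules to patients with an event open at exit.**

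- *Completes the study, non-serious event that is not an unexpected device effect.* Only 13.6.1 applies. Follow-up continues to resolution, chronicity or loss.
- *Completes the study, serious device effect.* Under 13.6.1 follow-up continues as above. Under 13.6.3 it may end at exit, 30 to 37 days after stimulation.
- *Withdraws, serious device effect.* Under 11.6.1 follow-up continues to resolution where possible. Under 13.6.3 it may end on withdrawal.

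The second and third cases each have two answers, and no section ranks the rules. If 13.6.3 is taken to prevail, the second patient has the shortest planned follow-up of any completer with an open event.

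**Step 4. An event first found at exit.** The follow-up x-ray window is 30 ± 7 days, so day 23 to day 37, and the film may be taken at the exit visit. A serious event first detected there could receive no further follow-up under 13.6.3. Sections 16.9 and 16.10 require new findings on events already reported to be passed on, but 13.6.3 leaves no planned source for them after exit.

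**Step 5. What depends on the stop rule.** The secondary safety endpoint is the percentage of patients with at least one serious device- or procedure-related event during the study. It counts occurrence, which is the same under either rule. The sample size and the capture test do not use adverse event outcomes. What changes is the duration and final outcome recorded for events open at exit.

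**The case against.** The strongest reply is that there is no real conflict. A protocol governs what is done while a patient is in the study, so 13.6.1 can be read as implicitly ending at exit, with 13.6.3 stating that limit openly. Serious and non-serious events would then stop at the same point. This reading is possible, but the text does not give it: 13.6.1 lists its stops and exit is not among them, and 11.6.1 shows that the protocol does expect events to be followed after a patient has left.

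A second reply runs the other way. Section 13.6.1 covers all adverse events, so the longer rule already protects serious ones. That too is possible, and it is why the documents do not support the stronger reading that serious events definitely receive less follow-up. That holds only if 13.6.3 overrides 13.6.1, and nothing says it does. The contrast is also not purely one of seriousness, because 13.6.3 names unexpected device effects as well.

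Third, a reader might infer that a permanent nerve injury could never be established in this study because the last visit falls at day 30 to 37. The documents give no time needed to judge permanence, and 13.6.1 expressly allows follow-up until an event is judged chronic. Permanence is also only one of several seriousness criteria, so a nerve injury can be classed as serious without waiting for it.

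These replies narrow the point. They do not say which rule a site should apply.

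**Conclusion.** The inconsistency stands. Three sections give different end points for following an unresolved event, and none says which prevails for a serious event or device effect still open at exit. The consequence is conditional: if a site applies 13.6.3, such an event could be left with an unknown final outcome 30 to 37 days after stimulation, while a non-serious event would still be followed.

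The effect is confined to the recorded outcome and duration of those events. A reader might infer that the reported safety result would change, but the planned safety percentage would be the same under either rule, and no sample size or test is affected. No figure can be put on the number of patients involved, because the documents give no expected rate of events open at exit. The point deserves correction because a first-in-human study should not leave the outcome of a serious device effect to each site's choice of section, and because the correction is cheap.

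**What to change.** Reconcile 13.6.3 with 13.6.1 and 11.6.1 so that a single stop rule applies, and cross-refer to it from all three sections. Under that rule, serious events and device effects open at exit should not be followed for less time than other adverse events. State also that outcomes learned after exit are recorded on the Adverse Event Form, so that duration and outcome are completed for events that were open at the last visit.

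The change is one sentence in 13.6.3 with matching cross-references. The running cost is occasional contact after exit with the few patients whose events remain open. No visit need be added for anyone else, and the analysis is untouched.
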